### 9.4.4 Supportive analyses

The primary and the secondary analyses will be repeated for the PPS.

The analysis results and the imputed data for different methods for imputing missing data will be compared.

In a sensitivity analysis, data will be analyzed in the same manner as for the primary analysis, but with missing data imputed using pattern mixture approach combining the jump to reference and the randomized-arm missing at random approaches (Carpenter, et al 2013) by distinguishing the following two cases:

1. A continued treatment effect for QAW039 150 mg patients being lost to follow-up for reasons likely to be unrelated to study drug (e.g. lost to follow-up, withdrew consent) will be assumed (randomized-arm missing at random).
2. Same treatment effect as placebo will be imputed for QAW039 150 mg patients that discontinue study drug and are lost to follow-up due to (or following a study drug discontinuation due to) lack of efficacy, adverse events or death (jump to reference).

If feasible, retrieved drop-out will be used to impute missing post-study drug discontinuation data as a sensitivity analysis. While retrieved drop-outs may be a particularly suitable basis for imputing data for non-retrieved drop-outs as it is most close to the ITT principal, this analysis may not be feasible or may require simplification of the imputation model, because observed post-study drug discontinuation data may be sparse.

The primary efficacy variable will also be analyzed using a repeated measurement analysis model in which treatment, age group (<18 vs. ≥18 years), use or non-use of a second asthma controller medication at study entry, region, visit (where FEV1 measurement is taken per

assessment schedule [Table 6-1](#)) and treatment-by-visit interaction will be included as fixed-effect factors, and baseline pre-dose FEV1 value as well as the baseline daytime asthma symptom score, baseline total daily SABA use and visit-by-baseline FEV1 as covariates. A common unstructured covariance matrix among visits for each treatment group will be used. The analysis will be performed based on all available on-treatment data up to week 12 and based on a likelihood method with an assumption of missing at random (MAR) for missing data assuming a hypothetical situation of continued treatment. On-treatment data is defined as all available data collected while patients took the study drug up to the Week 12 visit. The estimated treatment differences for all treatment comparisons will be tabulated along with the associated 95% confidence intervals and two-sided p-values.

In a tipping point analysis it will be explored by how much the imputed continuous missing data for the investigational and the placebo arm would have had to change compared to the imputations in the primary analysis in order to alter the trial conclusions. This will include an exploration of the possibility that patients with missing data from the investigational arm has worse outcomes than patients with missing data from the placebo arm.

In a further rank-based sensitivity analysis for the primary endpoint, patients will be ranked from smallest to largest in the following sequence with high ranks denoting greater efficacy.

1. patients that died
2. patients that withdrew from the trial
3. patients that completed the trial

Within category 3, patients with higher FEV1 change from baseline will be ranked greater than patients with lower change from baseline. Within categories 1 and 2, patients that withdraw from the trial later will get higher ranks than patients that withdraw early. In case patients withdraw at same study day, patients with higher FEV1 change from baseline at the last assessment are assigned a higher rank. In case of ties in the FEV1 values or no available post-baseline assessments of the primary variable, we use midranks. A Wilcoxon rank-sum test stratified by age group (<18 vs. ≥18 years), use or non-use of a second asthma controller medication, and region will be used to analyze the ranked data.

## Subgroups

The primary and secondary analyses will also be conducted by subgroup including for key demographic (e.g., age, sex, race, BMI, geographic region) and disease related subgroups (e.g. number of exacerbations in the previous year, use or non-use of a second asthma controller medication, baseline FEV1 tertiles, ACQ tertiles, XXXXXXXXXX).

## 9.5 Analysis of secondary variables

### 9.5.1 Efficacy variables

The secondary variables of this study are change from baseline in daytime asthma symptoms, change from baseline in total daily SABA use, and change from baseline in AQLQ+12 over the 12 weeks of treatment. The local significance level for each secondary null hypothesis will be determined based on the closed testing procedure specified by [Figure 9-1](#). A range of

sensitivity analyses will be conducted on secondary endpoints under different missing data handling approaches in a similar fashion as those described in [Section 9.4.4](#).

#### 9.5.1.1 Daytime asthma symptoms in patients

Daytime asthma symptoms are evaluated through four questions and each of them will be rated on a scale of 0 to 6. Higher scores indicate more severe asthma-related symptoms. A mean score will be calculated for the responses to 4 questions. The main analysis of the secondary endpoint of daytime symptoms will be performed for all patients over the entire age range (12 years and older). The baseline of daytime asthma symptoms will be defined as the average of the mean daytime asthma symptom score during the placebo run-in period. The mean of change from baseline in the daytime symptom scores over the 12 weeks of treatment will be analyzed using an analysis of covariance (ANCOVA) model in a similar fashion as the primary efficacy variable. The null hypothesis is that the treatment difference compared to placebo over the 12 weeks of treatment = 0, while the alternative hypothesis is that the treatment difference to placebo over the 12 weeks of treatment  $\neq$  0. This model will be fitted to each of multiple imputations generated using a jump-to-reference approach as for the primary analysis.

The asthma diary included in this study to measure daytime asthma symptoms was validated in studies of patients aged 18 to 65 years ([Santanello et al 1997](#)). It was subsequently included as a measure in placebo-controlled studies of montelukast in patients aged 15 years and older ([Reiss et al. 1998](#) and [Malmstrom et al. 1999](#)) and shown to be responsive to both montelukast and inhaled beclomethasone therapy in this age range. Given the performance characteristics, particularly the responsiveness to asthma therapies, of the asthma diary are known for patients aged 15 years and older, a supportive analysis of the secondary endpoint of daytime symptoms will be included and be limited to patients aged 15 years and older.

#### 9.5.1.2 Total daily use of SABA

Total daily use of SABA (the number of puffs taken in the previous 24 hours) by the patient will be analyzed using ePEF/ eDiary data. The baseline of SABA use will be defined as the average of total daily SABA use during the placebo run-in period. The mean of change from baseline in the total daily use of SABA over the 12 weeks of treatment will be analyzed using an ANCOVA model in a similar fashion as the primary efficacy variable. The null hypothesis is that the treatment difference compared to placebo over the 12 weeks of treatment = 0, while the alternative hypothesis is that the treatment difference to placebo over the 12 weeks of treatment  $\neq$  0. This model will be fitted to each of multiple imputations generated using a jump-to-reference approach as for the primary analysis.

#### 9.5.1.3 AQLQ+12

The change from baseline in AQLQ+12 at week 12 will be analyzed using an ANCOVA model in a similar fashion as the primary efficacy variable. The baseline of AQLQ+12 is defined as the last assessment prior to the first dose of study drug. Missing data of AQLQ+12 overall score will be imputed a jump-to-reference approach as for the primary analysis.

#### **9.5.1.4 Summary statistics for the secondary variables**

Summaries of absolute values and change from baseline in the three secondary variables will be presented by visit and by treatment group. Figures will be produced to visually show the mean and the mean change from baseline by visit over study period for each treatment group.

#### **9.5.2 Safety variables**

All safety data will be summarized for the safety set.

##### **9.5.2.1 Adverse events**

Adverse events after informed consent including asthma exacerbations will be summarized and listed.

Adverse events starting on or after the time of the first intake of study drug will be classified as treatment-emergent adverse events. Any adverse events that started during the study after informed consent before the time of the first intake of study drug will be classified as a prior adverse events and not included in tabulations of treatment emergent adverse events.

The following treatment emergent adverse event summaries will be produced, overall by system organ class and preferred term, overall by system organ class, preferred term and maximum severity, suspected drug-related adverse events by system organ class and preferred term, serious adverse events by system organ class and preferred term, and adverse events leading to permanent discontinuation of study-drug by system organ class and preferred term.

The number and percentage of patients with the most frequent AEs will be summarized by treatment.

Selected adverse events of special interest may be summarized and analyzed as well.

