## **7.2 Serious adverse events**

### **7.2.1 Definition of SAE**

An SAE is defined as any adverse event [appearance of (or worsening of any pre-existing)] undesirable sign(s), symptom(s) or medical condition(s) which meets any one of the following criteria:

- is fatal or life-threatening
- results in persistent or significant disability/incapacity
- constitutes a congenital anomaly/birth defect
- requires inpatient hospitalization or prolongation of existing hospitalization, unless hospitalization is for:
  - routine treatment or monitoring of the studied indication, not associated with any deterioration in condition (specify what this includes)
  - elective or pre-planned treatment for a pre-existing condition that is unrelated to the indication under study and has not worsened since signing the informed consent
  - treatment on an emergency outpatient basis for an event not fulfilling any of the definitions of a SAE given above and not resulting in hospital admission
  - social reasons and respite care in the absence of any deterioration in the patient's general condition
- is medically significant, e.g. defined as an event that jeopardizes the patient or may require medical or surgical intervention.

All malignant neoplasms will be assessed as serious under "medically significant" if other seriousness criteria are not met.

Life-threatening in the context of a SAE refers to a reaction in which the patient was at risk of death at the time of the reaction; it does not refer to a reaction that hypothetically might have caused death if it were more severe (please refer to Annex IV, ICH-E2D Guideline).

Medical and scientific judgment should be exercised in deciding whether other situations should be considered serious reactions, such as important medical events that might not be immediately life threatening or result in death or hospitalization but might jeopardize the patient or might require intervention to prevent one of the other outcomes listed above. Examples of such events are intensive treatment in an emergency room or at home for allergic bronchospasm, blood dyscrasias or convulsions that do not result in hospitalization or development of dependency or abuse (please refer to Annex IV, ICH-E2D Guideline).

Any suspected transmission via a medicinal product of an infectious agent is also considered a serious adverse reaction.

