### **7.2.2 SAE reporting**

To ensure patient safety, every SAE, regardless of causality, occurring after the patient has provided informed consent and until 30 days after the last study visit must be reported to Novartis safety within 24 hours of learning of its occurrence. Any SAEs experienced after the 30 day period after the last study visit should only be reported to Novartis safety if the investigator suspects a causal relationship to study treatment.

All follow-up information for the SAE including information on complications, progression of the initial SAE and recurrent episodes must be reported as follow-up to the original episode within 24 hours of the investigator receiving the follow-up information. An SAE occurring at a different time interval or otherwise considered completely unrelated to a previously reported one must be reported separately as a new event.

Information about all SAEs is collected and recorded on the Serious Adverse Event Report Form; all applicable sections of the form must be completed in order to provide a clinically thorough report. The investigator must assess the relationship of each SAE to *each specific component of study treatment, (if study treatment consists of several components)* complete the SAE Report Form in English, and submit the completed form within 24 hours to Novartis. Detailed instructions regarding the submission process and requirements for signature are to be found in the investigator folder provided to each site.

Follow-up information is submitted as instructed in the investigator folder. Each re-occurrence, complication, or progression of the original event must be reported as a follow-up to that event regardless of when it occurs. The follow-up information should describe whether the event has resolved or continues, if and how it was treated, whether the blind was broken or not, and whether the patient continued or withdrew from study participation.

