2.7.1 Adverse events (AEs)

All adverse events, including asthma exacerbations, coded with MedDRA using the most actual version at the time of database lock, will be listed. Unless otherwise specified, summaries will include treatment-emergent adverse events (TEAEs) only. AEs starting on or after the time of the first intake of study drug and not later than 7 days (30 days in the case of a serious AE) after the last intake of study drug will be classified as a TEAE. For those patients who enter the safety study (CQAW039A2315) directly after Visit 299, AEs (including serious AEs) starting after Visit 299 will not be considered as TEAEs in this study as they will be reported in CQAW039A2315.

As a general rule of censoring, patients who either completed the study or discontinue treatment prematurely and without the event of interest will be censored at the minimum out of the dates of last medication intake + 30 days, final visit date, and date of death. The number and percentage of patients who reported TEAEs will be summarized by primary system organ class (SOC), preferred term (PT), and treatment group for

- all adverse events (AEs)
- all AEs by maximum severity
- AEs suspected to be related to study drug
- AEs by standardized MedDRA query (SMQ) level
- serious AEs (SAEs)
- AEs leading to permanent study drug discontinuation
- AEs of special interest

Unless otherwise specified, primary system organ classes will be sorted alphabetically and, within each primary system organ class, the preferred terms will be sorted in descending order of frequency in the QAW039 150 mg once daily treatment group. If a patient reported more than one AE with the same preferred term, the AE will be counted only once. If a patient reported more than one AE within the same primary system organ class, the patient will be counted only once at the system organ class level.

In addition, the most frequent AEs will be presented by preferred term in descending order of frequency in the QAW039 150 mg once daily treatment group.

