2.7.2 Deaths

The number of deaths resulting from TEAEs will be summarized by SOC and PT. All the deaths in the clinical database including those occurring during screening will be listed.

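### Treatment-emergence is set by AE start date alone, so an event that began before the first double-blind dose and worsens on treatment misses the TEAE tables if it keeps its original onset date

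*Protocol*

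**What the plan says.** Protocol 9.5.2.1 sorts adverse events by onset: "Adverse events starting on or after the time of the first intake of study drug will be classified as treatment-emergent adverse events". An event that began after consent but before that intake "will be classified as a prior adverse events and not included in tabulations of treatment emergent adverse events". Neither sentence makes an exception for later worsening.

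SAP 2.7.1 gives the rule the analysis will follow. It takes "AEs starting on or after the time of the first intake of study drug and not later than 7 days" after the last intake, or 30 days for a serious event. For patients who enter the follow-on safety study, it stops at Visit 299. SAP Section 4 repeats this as a change from the protocol, and the change described there concerns only the end of the window. Unless otherwise specified, "summaries will include treatment-emergent adverse events (TEAEs) only".

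On deaths, SAP 2.7.2 says: "The number of deaths resulting from TEAEs will be summarized by SOC and PT". It adds: "All the deaths in the clinical database including those occurring during screening will be listed".

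On recording, Protocol 7.1 requires an AE, once detected, to be followed to resolution, with changes in its severity assessed at each visit. The items it asks for include a severity grade and start and end dates, but no date of a change in severity. For serious events, Protocol 7.2.2 says: "Each re-occurrence, complication, or progression of the original event must be reported as a follow-up to that event regardless of when it occurs". The SAE definition in Protocol 7.2.1 speaks of the "appearance of (or worsening of any pre-existing" sign, symptom or condition.

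**The concern.** Summaries of TEAEs are the adverse-event part of the safety endpoint (Protocol Table 2-1, SAP Table 1-1). Worsening of a complaint already present at first dose is one form a drug effect can take. Protocol 3.6 lists headache, palpitations, nausea, nasopharyngitis and dizziness among the potential side effects of QAW039, and complaints of this kind could be ongoing at randomization. A rule that looks only at the start date cannot count their worsening.

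The direction of the effect depends on the drug. If QAW039 worsens ongoing events, the uncounted cases fall mainly in the QAW039 arm and the comparison moves towards no difference. If worsening has nothing to do with the drug, randomization balances the omissions in expectation and both arms simply show lower counts. The documents do not say which applies.

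**Working it through.** The plan gives no figure to reproduce. The check applies its rules to one kind of event and follows it through each output.

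**Test case (hypothetical).** A mild headache starts in the placebo run-in, between Visit 101 (Day -7) and Day 1. It is ongoing at the first double-blind dose and is severe by Visit 203 (Day 28).

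**Step 1: classification.**
- Protocol 9.5.2.1: onset precedes first intake, so the event is prior.
- SAP 2.7.1 and Section 4: the event did not start on or after first intake, so it is not a TEAE. The 7-day and 30-day limits act only at the end of treatment and do not help.

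**Step 2: which date the event carries.** Protocol 7.1 treats a change in severity as something assessed within an AE already detected, which suggests one record with its original start date. No section instructs sites to open a new record or enter a new onset date on worsening. No section forbids it either, and the eCRF completion guidance is not among the documents. Step 3 therefore assumes that the original date is kept.

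**Step 3: outputs.**

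| Output | Event appears? |
|---|---|
| SAP 2.7.1 tables: all AEs, maximum severity, suspected related, SMQ, serious, leading to discontinuation, special interest | No |
| SAP 2.7.2 table of deaths from TEAEs (if fatal) | No |
| SAP 2.7.1 listing of all AEs | Yes |
| SAP 2.7.2 listing of all deaths (if fatal) | Yes |
| SAP 2.7.1.2 registry count of deaths from SAEs (if fatal) | Possibly: that sentence is not limited to treatment-emergent events |

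**Step 4: length of the window.** Table 6-1 puts Visit 1 at Day -21, which agrees with up to 2 weeks of screening plus 1 week of run-in: 14 + 7 = 21 days. Protocol 3.1 allows consent up to 14 days before Visit 1, so the longest window is 21 + 14 = 35 days.

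**Step 5: which first dose.** The protocol glossary includes placebo run-ins in the term study drug. Read that way, events starting in the run-in would already be treatment-emergent under 9.5.2.1, and the window would end at Day -7: 35 - 7 = 28 days at most. SAP 2.1.1.1 places the first dose at Day 1 (Visit 201), which restores the 35 days. The definition should therefore say double-blind.

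**Step 6: comparison with other safety data.** SAP 2.7.4.1 (QTcF) and 2.7.4.2 (vital signs) count notable values that are new or that worsen. The laboratory rule in 2.7.3.3 uses similar words, but it requires a baseline that is not notable even for a worsening value, so it does not clearly capture worsening from an abnormal baseline. For liver enzymes, the sentence on tabulation mentions only new abnormalities. The contrast with AEs is therefore clear for QTcF and vital signs and weak for laboratory data.

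**Number of patients.** The documents give no rate of AEs starting before the first dose, of those still ongoing at Day 1, or of worsening. No count can be computed.

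**The case against.** The strongest objection is that the loss is conditional. A reader might infer that every pre-dose event that worsens, including one that turns serious or fatal, drops out of every TEAE table. The documents do not support that. The progression sentence in Protocol 7.2.2 concerns SAEs already reported, and a non-serious event that turns serious has no earlier SAE report to follow up. The same section has an SAE at a different time interval reported as a new event. The SAE definition in 7.2.1 allows a serious worsening to be read as an event in its own right, with an onset on treatment, which would make it a TEAE. That definition concerns seriousness and does not contradict the TEAE rule. This part of the objection stands: the case is clearest for changes in severity and least certain for serious and fatal events.

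A second stronger inference is that the event is hidden. It is not. All AEs and all deaths are listed. SAP 2.4.1.1 shows reasons for stopping study treatment whatever the onset of the event. The DMC also reviews unblinded safety data (Protocol 8.4). What remains is that listings give no counts by arm, and reasons for discontinuation do not show the AE by preferred term. Protocol 9.5.2.1 does say that AEs after consent will be summarized, but the tables it then specifies by system organ class and preferred term are TEAE tables.

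A third is that a number of misclassified patients, or a bias of known size, can be stated. It would rest on invented rates. Eligibility also limits ongoing events. An exacerbation in screening or run-in makes the patient a failure (Protocol 3.1, 6.4.3), and a respiratory infection or asthma worsening in screening is handled by re-screening after recovery (Protocol 4.2).

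None of this supplies the missing clause. The uncertainty over how a worsening is dated is itself a reason to write the rule down.

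**Conclusion.** The point holds as a gap in the definition. Both documents make treatment-emergence a matter of start date. An AE that begins between consent and the first double-blind dose and then worsens is left out of the TEAE tables, and of the table of deaths from TEAEs if fatal, whenever its original onset date is kept.

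This rests on two things: the start-date rule, which is explicit, and retention of the onset date, which Protocol 7.1 suggests but no section states. If unseen eCRF guidance requires a new record at worsening, the event would be a TEAE and the gap would close in practice.

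The effect is confined to tabulation by arm. Events are still recorded and listed. The number of patients cannot be derived and is probably small, given a window of at most 35 days and the eligibility rules that screen out many respiratory events. The efficacy analysis, sample size and type I error are unaffected. The change is worth making because it costs little and concerns a stated safety endpoint.

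**What to change.** 1. In SAP 2.7.1, define a TEAE as an AE that starts on or after the first dose of double-blind study drug, or that started earlier and increases in severity, or becomes serious or fatal, on or after that dose. Keep the existing 7-day and 30-day windows and the Visit 299 cut, and apply them to the date of worsening for events with earlier onset.
2. State how the eCRF records the date of worsening. Either one record with a dated change in severity or seriousness, or a new record linked to the original, would serve. The choice must agree with follow-up within the event in Protocol 7.1 and with the SAE follow-up and new-event rules in Protocol 7.2.2. Without this date, the clause in item 1 cannot be programmed.
3. List the change in SAP Section 4, which already revises this definition. Aligning Protocol 9.5.2.1 itself would need a written amendment under Protocol 11.1.

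The cost is some added data entry at sites, minor programming and slightly higher TEAE counts. No extra patients or visits are needed.
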